### Statistics analysis of safety

After the first dose inoculation and the second dose inoculation, the number of adverse reactions (rate), number of cases and adverse reaction grade were recorded.

The number of adverse events after inoculation will be described.

Comparisons will be conducted to evaluate differences in response between study groups using a  $\chi^2$  test or Fisher's exact test to compare to the difference of adverse events rate. Statistical significance will be considered at a level of  $\alpha = 0.05$  and all tests will be 2-sided.

### Comparison of compliance

The rate of expulsion and the rate of drug combination will be described.

Comparisons will be conducted to evaluate differences in response between study groups using a  $\chi^2$  test or Fisher's exact test to compare to the difference of the rate of expulsion and the rate of drug combination. Statistical significance will be considered at a level of  $\alpha = 0.05$  and all tests will

be 2-sided.

## APPENDIX I. GRADING STANDARDS FOR SEVERITY OF SAFETY INFORMATION

The Event of clinical response and laboratory abnormalities after vaccination is judged by the China State Food and Drug Administration on "Guidelines for the classification of adverse events in vaccine clinical trials".

### Grading of Local Adverse Events

Local Adverse Reactions	Mild (Grade 1)	Moderate (Grade 2)	Severe (Grade 3)	Potential Life Threatened (Grade 4)
Pain	Resistance or withdrawal after contact or touch	Crying after touching or touching, but soothing	There is no comfort in continual crying	Require emergency or hospitalization
Induration	Diameter < 2.5 cm	Diameter $\geq$ 2.5cm, and area < 50% of the inoculated limb (anatomically, the limb where the inoculated site is located, such as the upper arm or thigh)	Area $\geq$ 50% of inoculated limb or ulceration or secondary infection or phlebitis or wound drainage	Abscesses, exfoliating dermatitis, and necrosis of the dermis or deep tissue
Redness	Diameter < 2.5 cm	Diameter $\geq$ 2.5cm, and area < 50% of the inoculated limb (anatomically, the limb where the inoculated site is located, such as the upper arm or thigh)	Area $\geq$ 50% of inoculated limb or ulceration or secondary infection or phlebitis or wound drainage	Abscesses, exfoliating dermatitis, and necrosis of the dermis or deep tissue

Rash Swelling	<15 mm and does not affect activity	15-30 mm or affect activity	>30 mm or limit daily activity	Gangrene
Itching	Itching at the site of inoculation was relieved by itself or within 48 hours after treatment	The site of inoculation was itchy, which did not relieve within 48 hours after treatment	Affect daily life	N/A

### Grading of Systemic Adverse Events

Systemic Adverse Reactions	Mild (Grade 1)	Moderate (Grade 2)	Severe (Grade 3)	Potential Life Threatened (Grade 4)
Fever	37.5-38.0°C	38.0-39.5°C	≥39.5°C	
Diarrhea	Mild or transient, 3 ~ 4 stools per day or mild diarrhea lasting for less than 1 weeks	Moderate or persistent, 5~7 times per day, or more than 1 week diarrhea	> 7 times of water stool per day, or blood diarrhea, orthostatic hypotension	Hypotension shock requiring hospitalization
Constipation	Need stool softener and diet adjustment	Need a laxative	Stubborn constipation needs to be dredge manually or use enema	Toxic megacolon or ileus
Dysphagia	Slight discomfort in swallowing	Diet restricted	Diet and conversation are very limited; Cannot eat solid food	No liquid food; Need intravenous nutrition
Anorexia	Decreased appetite, but not reduced food intake	Decreased appetite, decreased food intake, but no significant weight loss	Decreased appetite and significantly decreased body weight	Need for intervention(E.g., gastric feeding, parenteral nutrition)
Vomiting	1~2/24 hours with no impact on activities	3~5/24 hours or restricted activities	>6 times within 24 hours or intravenous rehydration is required	Hospitalize or other routes of nutrition are required because of hypotensive shock.

Nausea	Transient (<24 hours) or intermittent and basically normal food intake	Reduced food intake due to persistent nausea (24~48 hours)	Persistent nausea causes almost no food intake (>48 hours) or requires intravenous fluids	A threat to life(E.g. hypotensive shock)
muscle pain (Non-inoculated site)	Do not affect daily activities	Slightly affect daily activities	Severe muscle pain that severely affects daily activities	Emergency or hospitalize
Arthritis	Mild pain with inflammation, erythema or joint swelling; But without hindrance to function	Moderate pain with inflammation, erythema or joint swelling; Hinder function, but do not affect daily activities	Severe pain with inflammation, erythema or joint swelling; Impact on daily activities	Permanent and/or incapacitated joint injury
Arthralgia	Mild pain, no impairment of function	Moderate pain; Painkillers and/or pain are required to interfere with function, but do not affect daily activities	Severe pain; The need for painkillers and/or pain affects daily activities	Impotence pain
Headache	No effect on daily activities, no treatment required	Having a temporary effect on daily activities and may require treatment or intervention.	Seriously affecting daily activities, requiring treatment or intervention	Stubbornness, emergency or hospitalize
New convulsions	Duration of convulsions < 5 minutes, and status after convulsions <24 hours	Duration of convulsions $\geq 5 \sim < 20$ minutes, and status after convulsions <24 hours	Duration of convulsions $\geq 20$ minutes or status after convulsions >24 hours	Prolonged and multiple convulsions (e.g., status

				convulsions) or difficult to control (e.g., intractable epilepsy)
Cough	Transient, no treatment required	Keep coughing	Coughing, uncontrollable treatment	Emergency or hospitalize
Difficulty in breathing	Moving difficulty in breathing	Normal activity difficulty in breathing	Rest time difficulty in breathing	Difficulty in breathing, need oxygen therapy, hospitalize or assisted breathing
Pruritus at non-inoculated site (no skin damage)	Slightly itchy, not affecting or slightly affecting everyday life	Itching affects everyday life	Pruritus makes daily life impossible	NA
Abnormal mucous membrane of skin	Erythema/pruritus/color Change	Diffuse rash/maculopapular rash/dry/detritus	Blister/exudate/desquamate/ulcer	Exfoliative dermatitis involving mucosa, or erythema multiforme, or suspected Stevens-Johnsons syndrome
Insomnia *	Mild difficulty in falling asleep, not affecting or slightly affecting daily life	Moderate difficulty in falling asleep, affecting everyday life	Severe sleep difficulty, severe impact on daily life, need to be treated or hospitalize	NA
To provoke or inhibit.	Mild irritability or mild inhibition	Irritable or sleepy.	Unable to soothe or react poorly	NA

Acute allergic reaction **	Local urticaria (blister), no treatment required	Local urticaria, requiring treatment or mild angioedema, no treatment required	Extensive urticaria or angioedema requiring treatment or mild bronchospasm	Anaphylactic shock or life-threatening bronchospasm or laryngeal edema
Fatigue, fatigue	Do not affect daily activities	Affect normal daily activities	Seriously affect daily activities, unable to work	Emergency or hospitalize
Pain at non-inoculated site #(Location identified at the time of reporting)	Mild pain, not affecting or slightly affecting daily life	Pain affects everyday life	Pain does not work in everyday life	Disabling pain, loss of basic self-care

### Grading of Blood Biochemical

Serum	Mild (Grade 1)	Moderate (Grade 2)	Severe (Grade 3)	Potential Life Threatened (Grade 4)
Elevated liver function caused by AST ALT, influence factors	1.25-2.5 *ULN	2.6-5*ULN	5.1-10*ULN	>10*ULN
Creatinine	1.1-1.5*ULN	1.6-3.0*ULN	3.1-6*ULN	>6*ULN
Urea nitrogen (BUN)	1.25-2.5 *ULN	2.6-5*ULN	5.1-10*ULN	>10*ULN
Bilirubin: elevation caused by factors, but functional examination is normal	1.1-1.5*ULN	1.6-2.0*ULN	2.0-3.0*ULN	>3.0*ULN
Bilirubin: the increase caused by the factors associated with the increase of liver function test index	1.1-1.25*ULN	1.26-1.5*ULN	1.51-1.75*ULN	>1.75*ULN

### Grading of Blood Routine

Detection indicators	Level 1	Level 2	Level 3	Level 4
Liver function (ALT, AST increased)	1.25~<2.5 ×ULN	2.5~<5.0×ULN	5.0~<10×ULN	≥10×ULN
Total bilirubin increased (Mg/dL; Mmol/L )	1.1~<1.6×ULN	1.6~<2.6×ULN	2.6~5.0×ULN	≥5.0×ULN

### Grading of Urine Routine

Test Indicators/Grades	Level 1	Level 2	Level 3	Level 4
WBC (109/L)	11~<13	13~<15	15~<30	≥30
WBC (109/L)	2.000~2.499	1.500~1.999	1.000~1.499	<1.000
Lymphocyte Decrease (LY, 109/L)	0.75~1.00	0.5~0.749	0.25~0.49	<0.25

Neutropenia (ANC, 10  /L)	0.800~1.000	0.600~0.799	0.400~0.599	<0.400
Eosinophils (Eos, 10  /L)	0.65~1.5	1.51~5.0	>5.0	High eosinophil syndrome
Thrombocytopenia (PLT, 10  /L)	NA	50~75	25~49	<25
Low hemoglobin (g/dL)	9.5~10.4	8.5~<9.5	6.5~<8.5	<6.5

## **APPENDIX II. THE RELATIONSHIP BETWEEN ADVERSE EVENTS AND TRIAL VACCINES**

**Absolutely unrelated:** Because of other factors lead to adverse events, there is evidence that adverse events are caused by other causes, not related to vaccination.

**Possible unrelated:** Adverse events probable be caused by other factors, such as the clinical status of the subjects, other treatment or concomitant medication, inconsistent with the known adverse reactions of vaccination.

**Quite possible related:** Adverse events are consistent with known information of vaccine, and there is a causal relationship with the vaccine, not by other factors, such as the clinical status of the subjects, or other treatment with medication.

**Possible related:** Adverse events are consistent with known information of vaccine, and there is a causal relationship with the vaccine, not by other factors, such as the clinical status of the subjects, or other treatment with medication.

**Related:** Adverse events are consistent with known information of vaccine, and there is a causal relationship with the vaccine, not by other factors, such as the clinical status of the subjects, or other treatment with medication. In addition, adverse events will be repeated when subjects are tested with the vaccine.

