## **EVALUATION CRITERIA OF SAFETY**

The safety evaluation of each group will be divided into three stages. From the first dose inoculation to day 7 after inoculation; From the first dose inoculation to day 21 after inoculation; From the second dose inoculation to day 30 after the second dose inoculation. The first stage is the basis for the follow-up group of the same vaccine, and will be carried out under blind. The latter two stages are the basis for evaluation of vaccine safety, and will be carried out under unblind. If each evaluation is not found level 4 local and systemic adverse reactions associated with vaccine and the total incidence rate of level 3 of local and systemic adverse reactions and abnormal laboratory test which associated with the vaccination is lower than 15%, that the vaccine will be acceptable safety.

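### Appendix II gives two causality categories the same definition and keeps events with a plausible other cause out of every related category, so the safety verdict can turn on an unwritten coding choice

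*Combined protocol and SAP*

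**What the plan says.** Appendix II sorts adverse events into five categories: *Absolutely unrelated*, *Possible unrelated*, *Quite possible related*, *Possible related* and *Related*. The text under *Quite possible related* and *Possible related* is the same word for word: the event agrees with what is known of the vaccine, and "there is a causal relationship with the vaccine, not by other factors". *Related* repeats that text and adds recurrence on re-exposure. *Possible unrelated* lists a probable other cause and then adds "inconsistent with the known adverse reactions of vaccination". *Absolutely unrelated* applies where "there is evidence that adverse events are caused by other causes".

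The section Evaluation Criteria of Safety uses this coding. "The safety evaluation of each group will be divided into three stages", and the vaccine passes on two conditions. The first is "If each evaluation is not found level 4 local and systemic adverse reactions associated with vaccine". The second is that the total rate of grade 3 local and systemic reactions and "abnormal laboratory test which associated with the vaccination is lower than 15" per cent. The first stage is blinded. The other two, which the section names as the basis for judging vaccine safety, are unblinded.

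No section says which of the five categories count as associated with the vaccine, or what to do with an event that fits none of them.

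**The concern.** A causality scale normally keeps its lowest related grade for events that the vaccine may have caused but that something else could also explain. Here the label *Possible related* exists, but its definition excludes those events. In children aged 6-35 months such events are ordinary, for example a compatible symptom during an intercurrent illness whose role is suspected but not shown.

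The verdict on each group depends on counts of associated events, and the grade 4 limit is zero. If the text does not settle whether an event enters the count, two careful assessors can reach opposite verdicts on the same data. Because the deciding stages are evaluated unblinded, the question could be settled by someone who knows the group.

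**Working it through.** The documents state no grade 3 or grade 4 rate, so there is no figure of the plan's own to reproduce. The check compares the definitions and then applies the two limits.

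**1. The definitions side by side (Appendix II, paraphrased)**

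| Category | Fits known vaccine information? | Other cause |
|---|---|---|
| Absolutely unrelated | not stated | evidence of one |
| Possible unrelated | no | probable |
| Quite possible related | yes, and causal | none |
| Possible related | yes, and causal | none |
| Related | yes, and causal, and recurs | none |

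The third and fourth rows are the same. A string comparison of the two definitions confirms that they are identical.

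**2. An event that fits the vaccine and has a plausible, unproven other cause**

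- The three related categories exclude it, because each rules out other factors.
- *Absolutely unrelated* excludes it, because there is no evidence that the other cause produced it.
- *Possible unrelated*, if both of its conditions are required, excludes it too, and the event has no category.
- *Possible unrelated*, if either condition is enough and the other cause is taken as probable, includes it. The event is then coded unrelated and not counted.
- By its label, *Possible related* would count it, but the definition under that label does not allow this.

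**3. An event that does not fit known vaccine information and has no other cause identified**

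The related categories require consistency with vaccine information, and *Absolutely unrelated* requires evidence of another cause. *Possible unrelated* takes the event only on the either/or reading. It has no clear home.

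**4. Effect on the grade 4 limit**

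Let A be the clearly associated grade 4 events in a group and U the grade 4 events of the kinds in steps 2 and 3. If U is counted, the group fails when A + U ≥ 1. If not, it fails when A ≥ 1. The verdicts differ exactly when A = 0 and U ≥ 1, so one event is enough. Grade 4 does not always need an extreme clinical picture: for muscle pain, cough and fatigue the whole grade 4 entry in Appendix I is "emergency or hospitalize".

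**5. Effect on the grade 3 limit**

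Take the planned group sizes of 660 and 330 (design table under Safety observation) and assume that the rate is per child. The rate must be below 15%.

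- n = 660: 98/660 = 14.8% passes; 99/660 = 15.0% fails.
- n = 330: 49/330 = 14.8% passes; 50/330 = 15.2% fails.

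Let C be the children with a clearly associated grade 3 event and V the further children whose only grade 3 events are of the kinds in steps 2 and 3. For n = 660, coding changes the verdict only if C ≤ 98 and C + V ≥ 99. As an assumed illustration, C = 92 (13.9%) needs V = 99 - 92 = 7. For n = 330, C = 46 (13.9%) needs V = 50 - 46 = 4. Nothing in the documents suggests that the rate comes near 15%, so the grade 4 limit is the main exposure.

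**The case against.** **The duplicate may be a harmless slip.** If all three related labels count as associated, which is the natural reading, it does not matter which of two identical labels an event receives. This stands. A reader might infer that the duplicate by itself leaves the verdict open, and the documents do not support that. The problem is the events that the shared definition excludes.

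**The gap depends on the reading.** *Possible unrelated* is written as a list without a conjunction. Read as either/or, it can take both kinds of event. This also stands, so an exact count of unassigned event types should not be claimed. It does not remove the problem, because that reading leaves possible vaccine effects out of the safety count.

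**Examples must be chosen with care.** Cough during an infection is not automatically unclassifiable. If it is judged inconsistent with the vaccine and the infection is its probable cause, it is *Possible unrelated*. If the infection is shown to be the cause, it is *Absolutely unrelated*. Only the compatible symptom with an unproven cause falls outside the related categories as in step 2.

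**All adverse events are reported anyway.** The Safety endpoints and the safety statistics section include events regardless of cause, and coding cannot change those counts. This mitigates the problem but does not cure it. The verdict rests on associated events, and the statistics section mentions grade only for reactions: "the number of adverse reactions (rate), number of cases and adverse reaction grade were recorded".

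A reader might also infer from the empty grade 4 cell for fever that fever can affect only the grade 3 limit. That cell may have been lost in extraction, since other symptoms without a grade 4 are marked as not applicable, so nothing is built on it here.

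**Conclusion.** The point holds, and the rule should be corrected. Two causality categories are indistinguishable as written. No related category admits an event that fits the vaccine's profile but has a plausible, unproven other cause. The safety criteria do not say which categories count as associated. The duplication and the missing mapping are plain from the text. Whether the excluded event is unassigned or coded unrelated depends on how *Possible unrelated* is read, but on neither reading do the definitions count it as associated.

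The verdict is affected only if such events occur: one at grade 4 in a group with no other associated grade 4 event, or enough at grade 3 to cross 15%. The documents give no rates, so how likely this is cannot be estimated. A probability calculated from assumed per-child risks would only reflect the assumption. Nor do the documents show that causality itself is assigned unblinded. They show that the two deciding evaluations are unblinded, which is reason enough to settle the counting rule beforehand.

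**What to change.** 1. In Appendix II, define *Possible related* as a causal relationship that cannot be excluded although another factor could also explain the event. Keep the exclusion of other factors for *Quite possible related* and *Related* only.
2. Name one category for events that do not fit known vaccine information and have no other cause identified. If that category is *Possible related*, its definition must not require consistency with known vaccine information and must allow for the case where no other factor is found.
3. In Evaluation Criteria of Safety, state before unblinding that *Possible related*, *Quite possible related* and *Related* all count as vaccine-associated. Give adverse reaction the same meaning in the Safety endpoints and in the safety statistics section.
4. Report grade 3 and grade 4 events by group regardless of causality beside the verdict.

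The cost is a few lines of appendix text, a sentence in each section concerned, and one table. The drawback is that the related rate may rise by an amount the documents do not allow to be estimated, and a grade 4 event with a plausible other cause would count against the vaccine under the zero limit. The table regardless of causality puts such an event in context, and it is still useful if coding has already been done.
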